# 3. STUDY PROCEDURES

#### Study Design and Outcomes

This will be a prospective observational study comparing HR and RR of intraoperative surgical patients simultaneously recorded by standard intraoperative monitors and the ATLASense RAPHAEL PolyMonitor. Funding for this study will be provided internally. This study will fall under regulatory oversight by the FDA.

This study will consist of an initial chart review of patients scheduled to undergo elective procedures at Henry Ford Hospital – Main Campus from October 2021, to December 2021. The study team will review their medical record in EPIC prior to their scheduled procedure and screen them to ensure that they meet all eligibility requirements. Patients will be contacted at least one week prior to their scheduled

procedure to provide them with a brief introduction to the study. If they are interested, they will be sent an Informed Consent Form via mail or email (whichever is their preference). This will ensure that the patients have adequate time to review the consent form and ask questions prior to their procedure. They will then be consented in person prior to their procedure and given a copy of the signed consent form.

Our **primary study aim** is to determine if the ATLASense RAPHAEL PolyMonitor can reliably measure intraoperative HR and RR as compared to traditional intraoperative monitors. In order to evaluate this aim, our primary outcome will be bias and precision (95% limits of agreement) of HR and RR of the PolyMonitor compared with the traditional monitors. It is hypothesized that the ATLASense RAPHAEL PolyMonitor will provide HR and RR measurements within ± 10% of the reference monitor or ± 3 breaths/min or ± 5 beats/min .

A secondary outcome that will examined include technical reliability in terms of data loss occurrences, and data gap duration. Additional secondary outcomes include reliability in detecting bradycardia and tachycardia, as well as bias and precision (95% limits of agreement) of skin temperature and NIBP of the PolyMonitor compared with traditional monitors.

Further lessons include the logistics of employing this PolyMonitor in intraoperative setting including device placement, surgical practices that may impede data collection (body placement, etc), device placement, patient feedback on wearable, and patient positioning considerations.

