#### **Data Collection**

The information that will be pulled from patient charts in EPIC is as follows:

Age Gender Race Height Weight Pregnancy status BMI Planned surgery and associated diagnosis Allergies

Co-morbidities ASA status

On the day of surgery, the ATLASense RAPHAEL PolyMonitor will be placed on the patient's left chest mid sternal line in the operating room by the anesthesia provider. Traditional physiologic monitors including the GE E-PSMP-00 Monitor/Datex Ohmeda Aisys CS2: EKG HR, Ventilator RR, End Tidal CO2 RR, blood pressure cuff, \*\*\* core temperature probe will also be placed on the patient in the operating room.

Data acquisition will include: HR, RR, NIBP, core body temperature, data loss events (instances when data was not recorded/saved for any reason by the polymonitor or other monitors) and duration of data gaps, bradycardic events, and tachycardic events. Acquisition of data from the ATLASense PolyMonitor will be confirmed after the device is applied. Data will initially by tracked via medical record number (MRN). Following data acquisition, subjects will be deidentified using a random number generator to assign data sets for further data tracking.

Data will be collected via the ATLASense system and through the traditional operating room monitors, and this data will be time matched through synchronization of the monitors post hoc. Data collection intervals will be every 1 minute starting prior to induction of anesthesia and ending at the time of intraoperative monitor removal in the operating room. The ATLASense PolyMonitor will be removed at the same time as traditional physiologic monitors.

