# ATLASense RAPHAEL PolyMonitor – HR Detection

The electrocardiogram is recorded and processed to calculate the average HR by analyzing a single-lead electrocardiogram, which is preprocessed first to filter the raw electrocardiogram signal in order to minimize noise due to motion and muscle artifacts. Heart rate is measured using an algorithm developed by ATLASense.

The algorithm checks electrodes' contact to assure credibility, detects the R wave, computes several valid interbeat intervals, and computes the running HR with low latency. HR is calculated by computing inter-beat intervals (IBI), limiting IBI to one in every 300 mSec before the next beat (refractory period). The average HR is acquired by calculating the reciprocal of the average of 4 IBIs. Accuracy of resting HR is reported to be +/-1% or +/- 2 BPM, whichever is greater, and range of detection is reported to be from 30-240 BPM.

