# ATLASense RAPHAEL PolyMonitor – Temperature detection

The ATLASense RAPHAEL PolyMonitor detects skin temperature at up to 1 minute intervals, and derives measurements as an average based on multiple interval measurements. The latency period between measuring these intervals and calculating an average for data recording and display is ~ 1 second when employing a local server.

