### **CARESCAPE™ Monitor B850 – Temperature Measurement**

The Vyaire M1024215VY temperature sensor is a disposable device which can be inserted into a patient's esophagus and transmit core body temperature measurements at 1-minute intervals. The Vyaire M1024215VY has a direct input in order to display temperature information on the CARESCAPE™ Monitor B850.

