#### **Statistical Analysis**

The data pairs of HR and RR measurements obtained in 1-minute intervals derived from the wireless sensors and the traditional physiologic monitors will be analyzed using the Bland and Altman method for repeated measurements . The Bland and Altman method will also be used to account for within-subject variation by correcting for the differences across patients and the variance of differences between the average differences. The bias (mean difference) between the ATLASense RAPHAEL PolyMonitor sensors and reference monitor and the 95% limits of agreement (± 1.96 SD) will be determined for both HR and RR data.

PolyMonitor bradycardia and tachycardia alert notifications will be time matched with the HR measurements from the traditional monitor. Reliability in determining tachycardic and bradycardic events will be assessed by calculating sensitivity, specificity, positive predictive value and negative predictive value from paired data. True positive tachycardia will be defined as HR > 100 BPM via the traditional monitor. True positive bradycardia will be defined as HR < 60 BPM via the traditional monitor. Based on the data points from our primary aim (N=14303), we have 99% power to detect a change in sensitivity from 0.5 to 0.8 using a two-sided binomial test and 99% power to detect a change in specificity from 0.5 to 0.8 using a two-sided binomial test. The target significance level is 0.05. The prevalence of tachycardia and bradycardia is assumed to be 0.01 to  $0.02^{2,7}$ .

Data pairs for skin temperature and NIBP obtained in 1 to 5 minute intervals derived from the wireless sensors and the traditional physiologic monitors will be analyzed using the Bland and Altman method for repeated measurements . The Bland and Altman method will also be used to account for within-subject variation by correcting for the differences across patients and the variance of differences between the average differences. The bias (mean difference) between the ATLASense RAPHAEL PolyMonitor sensors and reference monitor and the 95% limits of agreement (± 1.96 SD) will be determined for both HR and RR data. Sample size calculation was estimated based on the primary study aim.

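### Skin temperature from the PolyMonitor is compared only with an oesophageal core probe, so the planned bias and limits of agreement measure departure from core, not sensor bias or precision

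*Combined protocol and SAP*

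**What the plan says.** Study Design and Outcomes lists among the secondary outcomes "bias and precision (95% limits of agreement) of skin temperature and NIBP of the PolyMonitor compared with traditional monitors". The same pair of terms, bias and precision, is used there for the HR and RR primary outcome.

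Statistical Analysis gives temperature and NIBP a paragraph of their own. The inputs are "Data pairs for skin temperature and NIBP obtained in 1 to 5 minute intervals derived from the wireless sensors and the traditional physiologic monitors", and the method is Bland-Altman for repeated measurements. The outputs are "The bias (mean difference) between the ATLASense RAPHAEL PolyMonitor sensors and reference monitor and the 95% limits of agreement", but the sentence ends "will be determined for both HR and RR data. Sample size calculation was estimated based on the primary study aim", so it names HR and RR where the paragraph concerns temperature and NIBP.

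The two temperature instruments are described separately:

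- **PolyMonitor (Temperature detection).** It "detects skin temperature at up to 1 minute intervals" and averages over several interval measurements. No conversion to core temperature is described.
- **Reference (CARESCAPE Monitor B850, Temperature Measurement).** The sensor goes into the "esophagus and transmit core body temperature measurements at 1-minute intervals". Data Collection agrees: a "core temperature probe will also be placed on the patient in the operating room".

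The acquisition list in Data Collection names core body temperature and no skin temperature. The aims in section 1 speak of body temperature without naming a site. No section describes a reference skin thermometer, a calibration or a bench check. No acceptance margin is given for temperature, whereas HR and RR each have one.

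**The concern.** For HR and RR, the wearable and the reference aim at the same quantity, so a mean difference can be read as device bias relative to the reference and the limits as a guide to precision. For temperature, the two instruments measure different quantities at different sites. A faultless skin sensor would still show a non-zero mean difference whenever average skin and core temperatures differ, and its limits would widen with any variation in that gap.

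At stake is how one reported result is read. The temperature outcome carries the same label as the HR and RR outcomes, for a device that section 1 describes as not yet validated. A large difference could be taken as a poor sensor when it is the gradient. A small one could be taken as a good sensor when a bias has offset part of the gradient.

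**Working it through.** The plan gives no expected bias, SD, margin or sample size for temperature, so there is no figure to reproduce. The check is whether the planned outputs determine sensor bias and precision.

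**Model.** Let G be true core minus true skin temperature, b the sensor bias, and e_s and e_c the sensor and core-probe errors. Take the core probe as unbiased and the components as independent. For each pair:

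- D = skin reading - core reading = b - G + e_s - e_c
- mean(D) = b - mean(G)
- var(D) = var(G) + var(e_s) + var(e_c)
- limits = mean(D) ± 1.96 × SD(D)

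The mean is one number with two unknowns. The variance is one number with three unknowns.

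**Illustration.** All °C values are assumed; none comes from the documents. The core-probe error SD is 0.1 throughout.

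| | Case A | Case B |
|---|---|---|
| Sensor bias b | 0 | -1.0 |
| Sensor SD | 0.2 | 0.5 |
| Gradient mean | 2.0 | 1.0 |
| Gradient SD | 0.5 | 0.2 |
| Mean difference | 0 - 2.0 = -2.0 | -1.0 - 1.0 = -2.0 |
| var(D) | 0.25 + 0.04 + 0.01 = 0.30 | 0.04 + 0.25 + 0.01 = 0.30 |
| Half-width | 1.96 × √0.30 = 1.07 | 1.96 × √0.30 = 1.07 |
| Limits | -3.07 to -0.93 | -3.07 to -0.93 |

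The cases were chosen so that the sums agree. They show that quite different sensors can give the same output, not that this will happen in the trial.

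**Does the repeated-measures method help?** It splits var(D) into between-patient and within-patient parts. The gradient and the sensor error can each vary at both levels, so each part is still a sum of the same unknowns. If every component is split equally between the levels, both cases have variance 0.15 at each level, an SD of √0.15 = 0.387.

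**Do more pairs help?** No. More pairs estimate mean(D) and var(D) more closely without adding an equation. For scale, 14,303 minutes of recording would give 14,303 temperature pairs at 1-minute spacing or about 2,860 at 5-minute spacing (14,303 / 5). The result is the same at either count.

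**Sensitivity of the limits to the gradient.** With sensor SD fixed at 0.2:

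- gradient SD 0: 1.96 × √(0.04 + 0.01) = 0.44 °C
- gradient SD 1.0: 1.96 × √(1.00 + 0.04 + 0.01) = 2.01 °C

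An unchanged sensor could thus show a half-width anywhere from 0.44 to 2.01 °C over this assumed range.

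**The case against.** The strongest reply is that the plan already defines bias as the mean difference from the reference monitor. In Bland-Altman usage that means disagreement between two methods, with no claim about sensor error. Section 1 says body temperature will be compared with standard monitors and that the device might one day replace several of them. For that question the skin-core gap is part of the disagreement to be measured, and nothing needs separating. The outcome is also secondary, with no hypothesis or margin.

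Much of this stands. Comparing skin with core is a legitimate question and the planned analysis answers it. What remains is that no section says this is the question, while the outcome wording matches that for HR and RR.

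Several stronger readings are tempting but not supported:

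- **That the protocol claims to validate the temperature sensor.** It does not; section 5 ties validation to heart rate and respiratory rate.
- **That the missing accuracy figure for temperature is the obstacle.** For HR the plan does state one ("Accuracy of resting HR is reported to be"), and likewise for RR, but these are symmetric tolerances for resting readings. A similar temperature figure would not be a signed bias that could be subtracted.
- **That temperature limits are not planned, because the sentence names HR and RR.** Study Design and Outcomes plans them; the phrase appears to have been carried over from the first paragraph of Statistical Analysis.
- **That core body temperature in Data Collection is a mistake.** It correctly names the reference variable; what the list lacks is the PolyMonitor skin reading. The asterisks just before the core probe may be an unfinished note or an extraction artefact, and supply no skin reference.

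**Conclusion.** The point holds in limited form. As designed, the temperature comparison can say how far the patch reading departs from oesophageal core temperature. It cannot give the bias or precision of the skin sensor. This follows from what the two instruments measure and does not depend on the number of pairs or the size of the gradient, provided that skin and core are not known to be equal.

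The size in this trial is unknown, because the documents give no gradient, SD or margin for temperature. The figures above rest on assumed values, an unbiased core probe and independent components; they illustrate the algebra and do not predict the result. One secondary outcome is affected. The HR and RR primary analysis and the target of 14,303 pairs are unchanged. The choice of blood pressure reference is outside this point.

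**What to change.** Three wording changes are enough:

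1. In Study Design and Outcomes and in Statistical Analysis, restate the temperature outcome as: *mean difference and 95% limits of agreement between PolyMonitor skin temperature and oesophageal core temperature, read as departure of the patch reading from core; temperature-sensor accuracy is not assessed.*
2. In the temperature and NIBP paragraph of Statistical Analysis, replace the closing reference to HR and RR data with *skin-minus-core temperature and NIBP*.
3. In Data Collection, keep core body temperature as the reference variable and add PolyMonitor skin temperature to the acquisition list.

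The data and the Bland-Altman method stay the same. The price is that no accuracy claim can be made for the temperature sensor. Such a claim would need a reference skin sensor beside the patch, which is new data collection and is not required here.

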# 4. ANTICIPATED RISKS

This study involves minimal risk for participants. The placement of the investigational device will not require deviation from standard practices. The risk to the participant includes breach of confidentiality in terms of inadvertent or unanticipated release of identifying information during the data acquisition process. The identifiable information will be stored in a secure REDCap database and will be destroyed as soon as possible after the record maintenance period. This risk will be mitigated by limiting data access to the principle investigator and co-investigators. Identifying information will be removed as soon as possible by a third party after the data acquisition process. All study data will remain on secure HFHS password-protected computers and stored on secure HFHS servers.

There is minimal to no risk with regards to placement of the study device. Risk may include allergic reaction upon placement of the device electrodes. This risk will be mitigated by excluding subjects with a known allergy to skin adhesive, and by monitoring the patient's skin following device placement and removal. In the event of an allergic reaction to the skin adhesive, the device will be removed, data collection will stop, and the patient will be treated as appropriate for an allergic reaction. The incidence will be documented in the study REDCap database. A member of the study team will follow up with the patient in recovery.

# 5. ANTICIPATED BENEFITS

There are no anticipated direct benefits to the patient. The research will allow for validation of the device in obtaining intraoperative heart rate and respiratory rate. The data will lay the foundation for further study of this device which may improve upon the standard intraoperative monitor and improve perioperative patient monitoring.

#### 6. RENUMERATION/COMPENSATION

No compensation or renumeration will be offered.

# 7. COSTS

There is no additional cost for participants associated with participation in this study.

# 8. ALTERNATIVES

The alternative is that subjects do not have to participate in the research.

# 9. CONSENT PROCESS AND DOCUMENTATION

This study consists of an initial chart review of information that is routinely collected as standard of care for all patients undergoing elective surgical procedures. Subjects deemed eligible for the study based on inclusion and exclusion criteria will be contacted and provided information about the study per a pre-determined telephone script. Subjects who are interested in participating will be sent the informed consent documents via mail or e-mail (per their preference) at least one week prior to their scheduled procedure. Patients will be provided the opportunity to privately ask questions by contacting research personnel prior to their scheduled procedure (via contact information provided on the informed consent form), as well as on the day of their procedure prior to placement of the device in the operating room.

Patients will be consented prior to their enrollment in the study by research personnel when they arrive to the hospital on the day of their procedure and provided with a copy of the signed consent. Physical copies will also be retained and held securely in a locked file within the department of anesthesiology office. After data collection is complete, records will be retained for the required record maintenance period before being destroyed.

# 10. WITHDRAWAL OF SUBJECTS

The subjects will be withdrawn from the research if the procedure cannot be completed for any reason. Subjects will also be withdrawn from the research if they indicate a desire to withdraw. If data acquisition has already begun or has been completed, data obtained will be destroyed along with any possible identifiers.

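### Section 10 destroys data and identifiers after withdrawal without exempting the adhesive-reaction record that section 4 requires

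*Combined protocol and SAP*

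**What the plan says.** Section 10 gives two routes to withdrawal. One is the patient's wish: "Subjects will also be withdrawn from the research if they indicate a desire to withdraw". The other needs no request: "The subjects will be withdrawn from the research if the procedure cannot be completed for any reason". One rule on data follows both: "If data acquisition has already begun or has been completed, data obtained will be destroyed along with any possible identifiers". It covers the case where recording is already complete, and it lists no exceptions.

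Section 4 (Anticipated Risks) deals with a reaction to the adhesive: "In the event of an allergic reaction to the skin adhesive, the device will be removed, data collection will stop". It then requires a record and a contact: "The incidence will be documented in the study REDCap database. A member of the study team will follow up with the patient in recovery". Section 11 adds that the REDCap database contains patient names and medical record numbers.

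Section 9 (Consent Process and Documentation) provides for signed consents to be stored and says that, once data collection is over, "records will be retained for the required record maintenance period before being destroyed". It makes no exception for withdrawn patients.

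**The concern.** Once a patient has withdrawn, a coordinator applying section 10 literally would delete what was obtained and every identifier. If that patient had a skin reaction, the entry made under section 4 either goes too or loses its link to a person. Deletion cannot be undone, so staff should not have to guess whether a safety record falls under the rule.

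Allergic reaction is the only physical risk of the device that the plan names, and section 1 describes the device as investigational and not yet validated. In a study of this size, the difference between one reaction and none can rest on a single record. Section 10 also does not ask for withdrawals to be counted or their reasons kept, so a reader of the results could not tell that a record had been lost.

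**Working it through.** This is mainly a check of the text. The plan states no figure for reactions or withdrawals, so there is nothing to reproduce.

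**Step 1: is there an exemption?** Sections 4, 9, 10, 11 and 12 were read for any statement that a safety record survives withdrawal. None has one. Section 12 sends issues to the IRB within one week, depending on their nature. That is a reporting route and does not say what is kept.

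**Step 2: what does the destruction rule cover?** Two readings are open.

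- *Plain reading.* Whatever was obtained from the patient is destroyed. The REDCap reaction entry was obtained during the study, so it goes.
- *Narrower reading.* The Data Collection part of section 3 lists what data acquisition includes: vital signs, data-loss events and gaps, and bradycardic and tachycardic events. Skin reactions are not on the list, so the rule might reach monitor data only. The reaction entry then stays. All identifiers are still destroyed, and by section 11 they sit in the same database. The entry can no longer be linked to a patient, a consent form or a follow-up contact.

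The first reading loses the event. The second keeps an event that cannot be traced.

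**Step 3: when would it apply?** By section 3, recording runs from before induction until the monitors come off in the operating room, in patients under general anesthesia. A request prompted by the device would therefore probably come in recovery or later. Section 10 covers that case, because its rule extends to completed acquisition. A reaction alone does not trigger destruction. Under section 4 it stops data collection and is documented, and the record is at risk only if withdrawal also occurs.

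**Step 4: illustration of size.** The planned number, 60-70, is from Project Timeline in section 3. The counts of reactions and withdrawals are assumptions. Intervals are exact (Clopper-Pearson) 95%. For 0 of n the upper limit is 1 − 0.025^(1/n). For 1 of n the lower limit is 1 − 0.975^(1/n), and the upper limit is the 97.5% quantile of Beta(2, n − 1).

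| Planned n | Reactions, all of whom withdraw | Full record | Record after destruction |
|---|---|---|---|
| 60 | 1 | 1/60 = 1.7% (0.0 to 8.9) | 0/59 = 0% (0 to 6.1) |
| 60 | 2 | 2/60 = 3.3% (0.4 to 11.5) | 0/58 = 0% (0 to 6.2) |
| 70 | 1 | 1/70 = 1.4% (0.0 to 7.7) | 0/69 = 0% (0 to 5.2) |
| 70 | 2 | 2/70 = 2.9% (0.3 to 9.9) | 0/68 = 0% (0 to 5.3) |

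For example, with n = 59 the upper limit is 1 − 0.025^(1/59) = 6.1%. At either end of the planned range, one patient is enough to move the record from one reaction to none, and the denominator falls by one as well.

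**The case against.** The best defence is that section 10 protects a patient's choice to leave, and that its wording need not reach safety records. Several parts of this stand.

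- A reader might infer that the plan expressly orders the reaction record destroyed. It does not. That follows from unqualified wording, and the list in section 3 allows the narrower reading.
- A reader might infer that sections 4, 9 and 10 can never all be followed. That is too strong. Documentation and the visit in recovery can both be done before a later withdrawal, and section 4 sets no retention period. The retention sentence in section 9 comes straight after the storage of signed consents and may concern those, or may be a general rule to which section 10 is the exception.
- A reader might infer that required feedback on the wearable is lost as well. Section 3 mentions "patient feedback on wearable, and patient positioning considerations" only among further lessons, with no instrument or time point, and it is not a primary or secondary outcome.
- A reader might infer that those who withdraw are the ones who object to the device, so that the safety record is shown to be biased. The link is plausible, but nothing in the documents supports it.
- The plan sets no safety endpoint and proposes no estimate of a reaction rate, so the table shows how sensitive such a statement would be and does not correct a planned result.
- The consent form was not available for this review and may already say what is kept.

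The defence does not supply an exemption. The narrower reading still leaves the entry unlinked, and neither reading preserves a count of withdrawals or the reasons for them.

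**Conclusion.** The point holds as a gap with a bad consequence. Section 10 states an unqualified destruction rule, and no other section protects the reaction record that section 4 requires. For a patient who reacts and then withdraws, the record is lost on the plain reading and unlinked on the narrower one.

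The illustrated effect is one reaction becoming none among 60-70 patients. It rests on an assumed reaction followed by a withdrawal, for which the documents give no rates. It does not depend on showing that dislike of the device drives withdrawal. The second route, a procedure that cannot be completed, leads to the same destruction without any request from the patient. This should be corrected, because the repair is small and a deletion cannot be reversed.

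**What to change.** In section 10, state that:

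- after a patient's request, destruction is limited to the vital-sign recordings;
- the signed consent, the date of withdrawal and any stated reason, and any device-reaction record are kept for the maintenance period in section 9;
- the number of withdrawals is reported, and these patients are counted in any statement about reactions.

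Say also what is kept when withdrawal follows an uncompleted procedure. At the least, the same records should be kept. Reconcile sections 4, 9 and 10, and make sure the consent form agrees.

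The cost is one or two sentences in section 10 and, if needed, in the consent form. The downside is that a minimal identifiable record is kept for patients who withdraw, and the consent form should tell them so.
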